7.4 Withdrawal of subjects

Subjects can leave the study at any time for any reason if they wish to do so without any consequences. The investigator can decide to withdraw a subject from the study for urgent medical reasons. Participation in the study is entirely voluntarily.

When necessary, the code of the administered medication can be broken to know with which medication the patient is treated.

7.5 Replacement of subjects in case of withdrawal

A dropout of 10-20% is taken into account. Results will still be included, unless the patient withdraws consent. Assessments that will be done at the withdrawal visit are adverse events, drug accountability and collect not-used study medication.

7.6 Premature termination of the study

Premature termination of the study may occur:

- a. if no positive decision is obtained with regard to the research or if the judgement of the competent medical research ethics committee that has assessed the research is irrevocably revoked;
- b. if a reasonable case can be made for terminating the research in the interests of the subjects' health.

8. SAFETY REPORTING

8.1 Temporary halt for reasons of subject safety

In accordance to section 10, subsection 4, of the WMO, the sponsor will suspend the study if there is sufficient ground that continuation of the study will jeopardise subject health or safety. The sponsor will notify the accredited METC without undue delay of a temporary halt including the reason for such an action. The study will be suspended pending further review by the accredited METC. The investigator will take care that all subjects are kept informed.

8.2 Aes, SAEs and SUSARs

8.2.1 Adverse events (AE)

Adverse events are defined as any undesirable experience occurring to a subject during the study, whether or not considered related to the investigational product. All adverse events reported spontaneously by the subject or observed by the investigator or his staff will be recorded

8.2.2 Serious adverse events (SAEs)

A serious adverse event is any untoward medical occurrence or effect that at any dose:

- results in death;
- is life threatening (at the time of the event);
- requires hospitalisation or prolongation of existing inpatients' hospitalisation;
- results in persistent or significant disability or incapacity;
- is a congenital anomaly or birth defect;
- Any other important medical event that may not result in death, be life threatening, or require hospitalization, may be considered a serious adverse experience when, based upon appropriate medical judgement, the event may jeopardize the subject or may require an intervention to prevent one of the outcomes listed above.

In the current study design, there is no expectation that the treatment will lead to Serious Adverse Events.

The sponsor will report the SAEs through the web portal *ToetsingOnline* to the accredited METC that approved the protocol, within 15 days after the sponsor has first knowledge of the serious adverse reactions.

SAEs that result in death or are life threatening should be reported expedited. The expedited reporting will occur not later than 7 days after the responsible investigator has first knowledge of the adverse reaction. This is for a preliminary report with another 8 days for completion of the report.

8.2.3 Suspected unexpected serious adverse reactions (SUSARs)

Adverse reactions are all untoward and unintended responses to an investigational product related to any dose administered.

Unexpected adverse reactions are SUSARs if the following three conditions are met:

1. the event must be serious (see chapter 9.2.2);
2. there must be a certain degree of probability that the event is a harmful and an undesirable reaction to the medicinal product under investigation, regardless of the administered dose;
3. the adverse reaction must be unexpected, that is to say, the nature and severity of the adverse reaction are not in agreement with the product information as recorded in:
 - Summary of Product Characteristics (SPC) for an authorised medicinal product;
 - Investigator's Brochure for an unauthorised medicinal product.

The sponsor will report expedited the following SUSARs through the web portal *ToetsingOnline* to the METC:

- SUSARs that have arisen in the clinical trial that was assessed by the METC;
- SUSARs that have arisen in other clinical trials of the same sponsor and with the same medicinal product, and that could have consequences for the safety of the subjects involved in the clinical trial that was assessed by the METC.

The remaining SUSARs are recorded in an overview list (line-listing) that will be submitted once every half year to the METC. This line-listing provides an overview of all SUSARs from the study medicine, accompanied by a brief report highlighting the

main points of concern. The expedited reporting of SUSARs through the web portal ToetsingOnline is sufficient as notification to the competent authority.

The sponsor will report expedited all SUSARs to the competent authorities in other Member States, according to the requirements of the Member States.

The expedited reporting will occur not later than 15 days after the sponsor has first knowledge of the adverse reactions. For fatal or life threatening cases the term will be maximal 7 days for a preliminary report with another 8 days for completion of the report.

The research coordinator at the corresponding centre will report the incident within 24 hours to the principal investigator followed by a written notification within 48 hours.

8.3 Annual safety report

A report of events, adverse events and serious adverse events will be combined with the annual progress report and be sent to the METC.

8.4 Follow up of adverse events

All adverse events will be continued until they disappear completely, or until a stable situation has been reached. Depending on the event, additional tests or medical procedures for followup can be required.

9. STATISTICAL ANALYSIS

9.1 Primary study parameter

Primary study parameter is change in hemoglobin level (mmol/L) between baseline and either 3 or 6 weeks postoperatively. Differences in change between the two experimental groups, and between each experimental group and the control group will be tested by use of the Student's T-test.

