4.4 Sample size calculation

This study will examine whether intravenous iron gives an improvement of the hemoglobin content 3 weeks postoperatively in patients with a hemoglobin between 5-7 mmol / L after caesarean sections, compared with giving oral iron, as well as placebo.

Based on the assumption that a minimum of 0,5 mmol/L difference in the hemoglobin level is thought to be of clinical importance and a standard deviation of 0,7 mmol/L (based on a retrospective analysis and a comparable study ⁴) it was determined that, with an alpha of 5% and a power of 80%, for each group 32 patients are needed. For 3 groups this means 96 patients. Allowing for patients lost to follow-up, the study number was set on 120 patients to guarantee adequate numbers of patients in each group.

A retrospective analysis performed at the Maastricht University Medical Centre between 1 January 2015 and June 30 2015, showed that 66 patients had a primary caesarean section. If we exclude the patients that had an operation on Friday (because during the weekends the study-medication cannot be prepared) the remaining number were 46 patients. Of these 46 patients, 31 people had a hemoglobin level between 5.0 and 7.0 mmol / L. If we assume that 70% of patients want to participate in the study, this will lead to 44 patients per year to randomize at the MUMC⁺. The other participating hospital (Zuyderland Sittard-Heerlen) has a double amount of deliveries including Caesarean sections which means that we need at maximum 1,5 year to complete the study.

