7. METHODS

7.1 Study parameters

7.1.1 Main study parameter

Hemoglobin level after 3 and 6 weeks.

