9.5 Alpha

We will employ an alpha of 5% (2-sided testing).

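### Neither the week nor the arm comparison that decides the trial is declared, so the false-positive rate of the primary claim is not fixed at 5%

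*Combined protocol and SAP*

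**What the plan says.** Section 9.1 defines the endpoint: "Primary study parameter is change in hemoglobin level (mmol/L) between baseline and either 3 or 6 weeks postoperatively". It then lists the tests: "Differences in change between the two experimental groups, and between each experimental group and the control group will be tested", by Student's t-test. That makes three pairs at each of two weeks. The main study parameter in section 7.1.1 is "Hemoglobin level after 3 and 6 weeks", and the Summary and section 2 also name both weeks without ranking them. On error control, section 9.5 says only "We will employ an alpha of 5% (2-sided testing".

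Section 4.4 is narrower. It says "This study will examine whether intravenous iron gives an improvement of the hemoglobin content 3 weeks postoperatively", "compared with giving oral iron, as well as placebo". Its calculation concludes that "with an alpha of 5% and a power of 80%, for each group 32 patients are needed". Section 1 instead poses the effect of oral iron and the effect of IV iron as separate questions.

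No section gives a testing order, a global test ahead of the pairwise tests, an adjustment, or a statement of which result makes the trial positive. The IV aim at week 3 in section 4.4 is not carried into section 9.

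**The concern.** Sections 1, 4.4 and 9.1 each support a different definition of a positive trial, and these definitions have different error rates. Because none is declared, the definition can be settled after the results are known, and a nominal p-value below 0.05 then has no known error rate behind it. A single significant result, for example oral against placebo at week 6 only, could be presented as a positive primary finding under section 9.1, although section 4.4 does not ask that question. Readers could not tell whether the rule came before or after the data. An analysis after unblinding cannot repair this.

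**Working it through.** **Inputs.** Difference 0.5 mmol/L, SD 0.7, two-sided alpha 5%, power 80%, 32 per group, 120 in total (section 4.4); dropout 10–20% (section 7.5); three pairs and two weeks (section 9.1).

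**The plan's own figure.** The normal approximation gives n = 2(1.960 + 0.842)² × 0.7² / 0.5² = 30.8, so 31 per arm. The t-test version gives 31.76, so 32, with power 80.3% at 32. Then 3 × 32 = 96, and 96 / (1 − 0.20) = 120. The plan's numbers reproduce, and they rest on one pairwise comparison at the full 5%.

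**Evaluable numbers.** 120 / 3 = 40 per arm, assuming equal allocation. This leaves 36 after 10% dropout and 32 after 20%.

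**False-positive rate by rule.** 100,000 simulated three-arm trials per setting; normal data, equal variances, 32 per arm, no true difference, pooled t-tests at 5%. Rho is the correlation between change to week 3 and change to week 6.

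| What counts as success | Rate |
|---|---|
| IV differs from both other arms, week 3 | 0.9% |
| One fixed pair, either week | 8–9% (rho 0.8 to 0.5) |
| Either IV comparison, week 3 | 9% |
| Any of three pairs, week 3 | 12% |
| Any of six tests | 18–21% (rho 0.8 to 0.5) |

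The first rule rises to at most about 5% when IV equals oral and placebo is far lower. The 12% agrees with the studentized range for three groups: P(range > 1.960 × √2) = 12.2%. Treating the tests as independent would overstate the rates: 1 − 0.95³ = 14.3% and 1 − 0.95⁶ = 26.5%.

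**The correlation.** The documents give none. If the three visits have equal variance σ² and equal correlation r, the covariance of the two changes is σ²(1 − r) and each variance is 2σ²(1 − r), so rho = 0.5. Carrying a week-3 value forward to a missing week 6 (section 9.6) raises rho. From rho 1 to rho 0, the six-test rate runs from 12% to 23%.

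**A global F-test at 5% before the pairwise tests, week 3 only.** With three arms, either all means are equal, and the F-test holds 5%, or at most one pair is equal, and that pair is tested at 5%. Simulated familywise error is 5.0% in both cases.

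Power per comparison, taking 0.7 as the SD of change:

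| Evaluable per arm | No gate | Gate, one or both irons +0.5 | Gate, IV vs placebo, oral halfway |
|---|---|---|---|
| 32 | 80% | 76% | 70% |
| 36 | 85% | 81–82% | 76% |
| 40 | 88% | 86% | 80% |

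With one or both irons at +0.5 and 32 per arm, Holm over the three pairs gives about 69% and Bonferroni 65%. For IV vs placebo with oral halfway, Holm gives about 66% against 70% for the gate. Null error rates do not depend on the SD, but power does. At 32 per arm with one or both irons at +0.5, the ungated and gated figures are 91% and 89% for SD 0.6, and 69% and 63% for SD 0.8.

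**The case against.** The strongest reply is that section 4.4 already supplies the rule. Read as IV having to beat both oral iron and placebo at week 3, it involves no inflation at all. That would settle the matter if it were declared, but section 4.4 states an aim. It does not say whether one or both comparisons must succeed, it is not repeated in section 9, and it conflicts with the two unranked primary weeks elsewhere.

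A second reply is that oral and IV iron are separate questions, each entitled to its own 5%. Whether different treatments sharing a placebo need familywise control is debated, and this point stands: one pair per question at one fixed week does hold 5% for that question. The plan fixes no week, however, and one pair tested at either week already runs at 8–9%.

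A reader might go further and infer that the trial has a false-positive rate of 18–21%. The documents do not support that. It requires that any of six significant tests counts as success, which the plan does not state, and a correlation that it does not give.

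**Conclusion.** The concern holds in this form: the deciding week and the deciding comparison are undeclared, and the false-positive rate of the primary claim depends on which rule is later adopted. Across the rules that the text allows, it runs from about 1% to 18–21% under the complete null, with the upper range resting on an assumed correlation of 0.8 to 0.5. The 12% for any pair at week 3 needs no correlation. This is more than missing detail, because the six tests as written, each at 5%, do not hold 5% overall. It does not follow that every permissible reading is inflated.

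The figures assume normal data, equal variances, equal arms and unadjusted t-tests. The optional change to regression in section 9.3 is not modelled. Section 4.4 describes a "difference in the hemoglobin level is thought to be of clinical importance and a standard deviation of 0,7 mmol/L", so whether 0.7 is the SD of level or of change is unclear; the power figures take it as change.

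**What to change.** Before unblinding:

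- **Section 9.1.** Name change in hemoglobin from baseline to week 3, the time point in section 4.4, as the single primary endpoint and week 6 as key secondary. Declare which comparison or comparisons decide the trial. Align the Summary and sections 2 and 7.1.1.
- **If all three pairs are to support claims.** Test them at two-sided 5% only after a global F-test of the three arms is significant at 5%. If the regression in section 9.3 replaces the t-test, use its overall test of arm. Holm over the three pairs is a simple alternative with less power.
- **Section 4.4.** State that 80% is the power of one unadjusted comparison at 32 evaluable per arm, and give the gated power at 32 and 36 from the table. Label any figure at 40 per arm as an upper case that assumes no dropout and no dilution from carried-forward values. Say whether the SD of 0.7 refers to level or change.

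The cost is a protocol amendment and no extra patients. At 32 per arm the gate takes about 4 points of power per comparison (80% to 76%), or about 10 for IV against placebo if oral lies halfway (80% to 70%). Week 6 becomes supportive, with estimates and confidence intervals still reported.

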Anemia after caesarean section is often treated with iron therapy to ensure that the hemoglobin will return to normal more rapidly. Scientific evidence for this action is limited. Several studies, in which iron therapy was given after orthopaedic or cardiac surgery, show that after 6 to 10 weeks the hemoglobin was not significantly different between patients treated with oral preparations and patients treated with a placebo.

These studies have not examined the hemoglobin level during the first few weeks after surgery including the quality of life analysis.

The purpose of this double blind randomized controlled trial therefore is to examine the effect of both oral iron therapy and intravenous iron therapy on hemoglobin level and on the quality of life during the first few weeks postcaesarean in patients with a moderate anemia.

Study design

Double blind randomized controlled trial

Study population

Patients fulfilling the in- and exclusion criteria with a hemoglobin level between 5.0 and 7.0 mmol/L after caesarean sections.

Intervention

Patients will be randomized into three groups:

1. Treatment with ferrous fumarate 200 mg 2dd 1 capsule during 30 days. These patients also get once a placebo intravenously.
2. Treatment with Ferinject[®]. These patients also obtain 60 placebo capsules for 30 days.
3. Placebo treatment: both a placebo intravenously and 60 placebo capsules for 30 days.

Main study parameters

Primary objective: Hemoglobin levels after 3 and 6 weeks

Secondary objectives:

- Quality of life after 1, 3 and 6 weeks
- Side effects of the medication
- Predictive value of other parameters such as CRP, transferrin, ferritin and hepcidin
- Cost analysis

Nature and extent of the burden and risks associated with participation, benefit and group relatedness

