2. OBJECTIVES

Primary objective:

Comparison of the hemoglobin level 3 and 6 weeks postoperatively between the different groups

Secondary objectives:

- Comparison of quality of life after 1, 3 and 6 weeks postoperatively between the different groups
- Comparison of the side-effects of various drugs
- Is there a “subgroup” of patients who have the greatest effect of the medication used (eg patients with low ferritin)
- Is there a “subgroup” of patients who respond better to ferinject than ferrous fumarate and vice versa (eg patients with elevated CRP).
- What are the costs of taking oral iron or intravenous iron

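### The primary variable is the hemoglobin level in the Summary, 2 and 7.1.1 but change from an unnamed baseline in 9.1, and 4.4 does not say which of the two its SD of 0.7 describes

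*Combined protocol and SAP*

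**What the plan says.** Three places define the primary variable as a level at follow-up:

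- Summary, main study parameters: "Primary objective: Hemoglobin levels after 3 and 6 weeks".
- Section 2: "Comparison of the hemoglobin level 3 and 6 weeks postoperatively between the different groups".
- Section 7.1.1: "Hemoglobin level after 3 and 6 weeks".

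Section 9.1 defines it as a change: "Primary study parameter is change in hemoglobin level (mmol/L) between baseline and either 3 or 6 weeks postoperatively". It then assigns an unadjusted t-test to that change, for all three pairs of arms: "Differences in change between the two experimental groups, and between each experimental group and the control group will be tested by use of the Student's". It does not say which hemoglobin is the baseline, and Annex 1 schedules both a pre-operative and a post-operative value.

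Section 4.4 sizes the trial on "a minimum of 0,5 mmol/L difference in the hemoglobin level is thought to be of clinical importance and a standard deviation of 0,7 mmol/L", with alpha 5%, power 80% and 32 patients per group. The same section states the aim as "whether intravenous iron gives an improvement of the hemoglobin content 3 weeks postoperatively", which can be read as level or as change. The 0.7 is attributed to retrospective data and a comparable study, and is not labelled as the SD of either variable. No baseline SD and no correlation between baseline and follow-up are given.

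Sections 9.2 and 9.3 replace the t-test by linear regression only if baseline imbalance is judged to matter for prognosis. They give no threshold and name no covariates. Section 7.2 minimises on post-operative hemoglobin in two strata, among other factors.

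**The concern.** Randomisation gives level and change the same expected difference between arms. It does not give them the same SD, and an unadjusted t-test on one is a different test from an unadjusted t-test on the other. Two things follow.

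First, a reader cannot tell whether the 80% in 4.4 describes the test in 9.1. It does if 0.7 is the SD of change. If 0.7 is the SD of level, the power depends on two quantities that the plan does not state.

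Second, a result significant for change but not for level, or the reverse, would leave the primary result open to dispute, because the objectives point one way and the analysis section the other. The conditional switch in 9.3 does not settle this: it is decided after the baseline data are seen, and the default remains the unadjusted test on change.

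**Working it through.** **Inputs.** From 4.4 and 9.5: difference 0.5 mmol/L, SD 0.7, two-sided alpha 5%, 32 per arm. Assumed, because the plan gives neither: baseline SD s0 from 0.4 to 0.57, and correlation r between baseline and follow-up from 0 to 0.7. As a guide to s0, hemoglobin spread evenly over the eligible range of 5-7 would have SD 2/√12 = 0.58.

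**The plan's figure.** A two-sample t-test with standardised difference 0.5/0.7 = 0.714 needs 31.8, so 32 per arm, and has 80.3% power there. The 32 reproduces for whichever variable has SD 0.7.

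**Case A: 0.7 is the SD of change.** The 80% then belongs to the test in 9.1, and only the wording of the endpoint conflicts.

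**Case B: 0.7 is the SD of level.** Then SD of change = √(0.7² + s0² − 2·r·0.7·s0). For s0 = 0.5 and r = 0.2 this is √(0.49 + 0.25 − 0.14) = 0.775, and the power is 72.0%. Power of the t-test on change at 32 per arm (%):

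| s0 | r = 0 | 0.2 | 0.3 | 0.4 | 0.5 | 0.6 | 0.7 |
|---|---|---|---|---|---|---|---|
| 0.40 | 68.5 | 76.6 | 80.9 | 85.5 | 89.9 | 94.0 | 97.2 |
| 0.50 | 62.9 | 72.0 | 77.2 | 82.7 | 88.3 | 93.6 | 97.6 |
| 0.57 | 58.8 | 68.2 | 73.7 | 79.9 | 86.3 | 92.4 | 97.3 |

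Change has less power than level only when s0² > 2·r·0.7·s0, that is when r < s0/1.4: below 0.29, 0.36 and 0.41 for the three rows.

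**How often the two t-tests disagree.** I simulated normal data with 32 per arm, true difference 0.5, s0 = 0.5 and r from 0 to 0.7. Under simple randomisation one test was significant and the other not in roughly 15-23% of trials. With arms exactly balanced on two hemoglobin strata the figure was roughly 10-18%. It moves with s0: over 0.4 to 0.57 the balanced figure runs from about 8% to 22%. With no true difference, at least one of the two tests was significant in about 8% of trials under simple randomisation and in about 5-6% with balanced strata, for one comparison at one week.

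**Adjusted model.** Fit Y = a + τ·arm + β·B + error, where B is the day-1 hemoglobin. Subtracting B from both sides gives Y − B = a + τ·arm + (β − 1)·B + error. The treatment estimate τ, its standard error and its p-value are therefore identical for level and for change. In case B the residual SD is 0.7·√(1 − r²), and power at 32 per arm is 80.3, 81.9, 83.9, 86.6, 90.1, 94.0 and 97.6% for the seven values of r above.

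**The case against.** The strongest reply is that only 9.1 assigns a test, and it assigns it to change. The other sections name a parameter or objective and prescribe no analysis, so reporting a t-test on level would depart from 9.1. This has force: 9.1 governs the test. It does not remove the conflict over which variable the primary claim concerns.

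The baseline can also largely be inferred. Section 9.4 places the questionnaire baseline on the first post-operative day before medication, 7.3 takes blood on day 1 before treatment, and eligibility and minimisation use the post-operative value. That is a fair reading, but 9.1 should state it.

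A reader might infer three stronger things, none of which the documents support:

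- *That the 80% belongs to level, so the planned test is underpowered.* Section 4.4 does not label the 0.7. Even if it is the SD of level, change is the more powerful variable once r exceeds s0/1.4. If close to 40 per arm (120/3) are analysed, change with s0 = 0.5 has 73%, 81% and 94% power at r = 0, 0.2 and 0.5, before any effect of the imputation in 9.6.
- *That the ambiguity raises the false-positive rate to about 8%.* That figure ignores the minimisation in 7.2. With the two strata balanced it is about 5-6%. Exact balance idealises minimisation over five factors, so the truth probably lies between the two, but the inflation is small.
- *That the two definitions can reach opposite conclusions.* Both estimate the same difference. What can differ is whether p falls below 0.05.

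**Conclusion.** The inconsistency is real and stands in the current text: level in three places, change from an unnamed baseline in 9.1, and an unlabelled SD in 4.4. The supportable conclusion on power is that the stated 80% cannot be tied to the test in 9.1. If 0.7 is the SD of level, power at 32 per arm lies anywhere from about 59% to 98% over the assumed baseline SD and correlation, so the direction of any error is unknown.

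The practical cost is a primary result that may depend on the definition: with a true 0.5 difference, roughly one trial in ten to one in six at baseline SD 0.5 with balanced strata, and somewhat more under simple randomisation. These rates rest on normal data and on baseline SD and correlation values that the plan does not supply. The point should be corrected because the remedy is cheap. It does not show that the trial is too small.

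**What to change.** 1. In 9.1, replace the t-test unconditionally with a linear model for hemoglobin at a named follow-up week, with treatment arm and the day-1 post-operative, pre-treatment hemoglobin as covariate. Remove the data-dependent switch in 9.2 and 9.3 for this analysis.
2. Name that day-1 value as the baseline and name the week. Section 4.4 is written around week 3.
3. Use the same primary variable in the Summary, 2, 7.1.1, 4.4 and 9.1.
4. In 4.4, say whether 0.7 is the SD of level or of change. Restate the power if it does not describe the planned analysis, giving the assumed correlation. If 0.7 is the SD of level, the adjusted model has 80-98% power at 32 per arm for r = 0-0.7.

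Merely declaring the level primary and leaving change descriptive would be weaker. It leaves the baseline value unused, and it keeps the 80% only if 0.7 is the SD of level.

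Cost: wording in five sections, the deletion in 9.2 and 9.3, and one power statement, which may change. No extra patients or measurements are needed, since the day-1 hemoglobin is already collected.

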3. STUDY DESIGN

The study will be a double blind randomized controlled trial.

Patients undergoing a primary caesarean section in the Maastricht University Medical Centre and the Orbis Medical Centre in Sittard will be informed about the study, both in writing and orally. A schematic overview of assessments is given in the schedule at the end of the protocol (annex 1).

If the patient has signed the informed consent the patient data will be entered in a database and then the pre-operative blood will be taken (standard and extra). If the postoperative hemoglobin level is between 5-7 mmol/L the patient will be randomized and two extra blood tubes will be taken. Randomization will be done by the computer and the first questionnaire will be completed. The patient characteristics will be copied from the electronic patient record. Subsequently, each patient will receive an infusion with a placebo or with Ferinject[®] (depending on which group the patient ended up). The patients will not know the actual treatment, because the infusion line and the flask with NaCl or Ferinject[®] will be packed. Also the venflon will be covered by a gauze. So both the patient and the doctor will not know if a placebo or the Ferinject[®] itself is given. The patient will receive 60 capsules to take home, which need to be taken two times daily. This can be ferrous fumarate or a placebo. To verify compliance, patients will use a dispenser which count how often it is opened. Postoperatively, the hemoglobin will be determined another two times: after 3 and 6 weeks. At 3 weeks the research nurse will do this at the patient's home and the second time this will be obtained in the hospital where it can be combined with the regular control. The research nurse will call the patient after 1 week to ask how things are going and whether the second questionnaire has been completed. If the nurse visits the patient after 3 weeks, she will ensure that the questionnaires about the quality of life after 1 and 3 weeks were completed. The day the patient will come for the regular check at 6 weeks, she will also be seen by the research nurse who will check whether the last questionnaire was also completed. At this appointment the hemoglobin and other blood-values will also be determined.

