During the pre-operative visit the informed consent will be signed. Normally this will be at the time of admission. The maximum time period between the pre-operative visit and the actual surgery may be 72 hours. In case the scheduled surgery is postponed to a time

point outside the allowed time window, the first pre-operative hemoglobin of the patient will be determined again.

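### Pre-operative Hb is collected but named in no analysis, and adjustment depends on observed imbalance, so available precision on the primary outcome may be lost

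*Combined protocol and SAP*

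**What the plan says.** **Collection.** Section 3 states that once consent is signed "the pre-operative blood will be taken (standard and extra". If surgery is postponed beyond the allowed 72 hours, "the first pre-operative hemoglobin of the patient will be determined again". Annex 1 marks Hb pre-operatively, on post-operative day 1, and at weeks 3 and 6. The pre-operative mark does not carry the footnote that limits other items to women with a post-operative Hb of 5 to 7 mmol/L.

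**Primary analysis.** Section 9.1 takes change in Hb from baseline to week 3 or week 6 and says "Differences in change between the two experimental groups, and between each experimental group and the control group will be tested" by Student's t-test. It names no covariate and does not say which Hb is the baseline.

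**Conditional analysis.** Section 9.2 compares baseline variables, Hb among them, descriptively. Section 9.3 replaces the t-test with multivariable linear regression only when baseline differences of prognostic importance appear. It lists no covariates.

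**Sample size.** Section 4.4 assumes that "a minimum of 0,5 mmol/L difference in the hemoglobin level is thought to be of clinical importance" and uses "a standard deviation of 0,7 mmol/L (based on a retrospective analysis and a comparable study". It concludes that "with an alpha of 5% and a power of 80%, for each group 32 patients are needed". Section 9.5 adds "We will employ an alpha of 5% (2-sided testing".

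**The concern.** Women entered this trial with different Hb levels before they bled, and part of the spread in Hb at weeks 3 and 6 may reflect that. Eligibility confines day-1 Hb to a 2 mmol/L band (5 to 7), which tends to weaken its link with later values. Pre-operative Hb is not selected on directly, so it may add information that day-1 Hb does not carry. That is a reason to expect some gain, not evidence of its size.

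To the extent that pre-operative Hb is prognostic, leaving it out keeps explainable variation in the error term. The intervals for IV versus oral, IV versus placebo and oral versus placebo are then wider than the collected data require. The imbalance trigger in 9.3 does not recover this, because precision is gained from a prognostic covariate whether or not the arms differ on it. The trigger also leaves the primary model to be chosen after the baseline data have been inspected.

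**Working it through.** **1. The plan's own figure.** Inputs from sections 4.4 and 9.5: difference 0.5 mmol/L, SD 0.7 mmol/L, two-sided alpha 5%, power 80%.

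- Normal approximation: n = 2 × [0.7 × (1.960 + 0.842) / 0.5]² = 30.77, so 31 per group.
- Exact t-test: 31.76, so 32 per group. This matches the plan. "For 3 groups this means 96 patients" also follows, since 3 × 32 = 96.
- Loss to follow-up: 96 / (1 − 0.20) = 120, or 40 per group. Section 7.5 gives 10 to 20% dropout.
- Power by t-test: 80.3% at 32 per group; 88.4% at 40 per group if no one is lost and the SD of 0.7 holds.

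**2. Which Hb is baseline?** The only explicit definition is in section 9.4, for quality of life: the first post-operative day, before study medication. The minimisation bands in section 7.2 (5.0–6.0 and 6.1–7.0) lie within the post-operative entry range. Day 1 is the natural reading of 9.1, but 9.1 does not state it.

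**3. Change score against day-1 adjustment.** Let X be day-1 Hb, Y later Hb, and ρ their correlation.

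- Change score variance: σY² + σX² − 2ρσXσY.
- Variance after linear adjustment for X: σY²(1 − ρ²).
- Difference: (σX − ρσY)², which is never negative.

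With equal SDs, as a multiple of σY²:

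| ρ | Change score, 2(1 − ρ) | Adjusted, 1 − ρ² |
|---|---|---|
| 0.3 | 1.40 | 0.91 |
| 0.5 | 1.00 | 0.75 |
| 0.7 | 0.60 | 0.51 |

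Day-1 adjustment therefore never does worse than the change score, apart from the degree of freedom used.

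**4. Adding pre-operative Hb.** Let r be the partial correlation of pre-operative Hb with later Hb, given day-1 Hb. The day-1-adjusted variance is multiplied by (1 − r²), and interval width by √(1 − r²). The documents give no r, so the range below is an assumption.

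| Assumed r | Variance reduction | Interval narrower by | Equivalent extra patients, 1/(1 − r²) − 1 |
|---|---|---|---|
| 0 | 0% | 0% | 0% |
| 0.2 | 4% | 2.0% | 4% |
| 0.3 | 9% | 4.6% | 10% |
| 0.4 | 16% | 8.3% | 19% |

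**5. Day-1 Hb must stay in the model.** Pre-operative Hb alone leaves σY²(1 − ρp²), where ρp is its own correlation with later Hb. In the ρ = 0.7 row of step 3 the planned change score leaves 0.60. Pre-operative Hb alone would beat that only if ρp exceeded √0.40 = 0.63. Replacing the change score by pre-operative Hb alone could therefore lose precision.

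**The case against.** The strongest reply is that this is an optional refinement of unknown size. No r is given, and r near zero, with no gain, is not excluded. Even at r = 0.4 the interval narrows by only about 8%. The plan has 80.3% power at 32 per group and enrols 40. No bias or inflated error rate is at issue. The larger weaknesses are the undefined baseline, the unadjusted change score and the imbalance-triggered regression. All of this stands. It limits the size of the point and shapes the fix, which has to deal with those weaknesses together.

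Three stronger readings are tempting and are not supported:

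- **That no analysis uses pre-operative Hb.** Section 9.2 could tabulate it and a section 9.3 regression could include it. Because 9.1 leaves baseline Hb undefined, even a change from the pre-operative value is not strictly excluded. What the text supports is that no analysis names it.
- **That power at 32 per group would rise from 80% to about 82–87%.** Those figures come from multiplying the SD of 0.7 by √(1 − r²) for r of 0.2 to 0.4. But r is conditional on day-1 Hb, and section 4.4 does not describe 0.7 as conditional on day-1 Hb, nor say whether it is the SD of the level or of the change. The result is neither the gain over the planned test nor the gain over a day-1-adjusted model.
- **That the trial is underpowered without the covariate.** On its own inputs, for a single comparison, it is not.

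**Conclusion.** The point holds as a low-cost improvement. An already collected baseline value is named in no planned analysis, and adjustment of any kind depends on observed imbalance with unnamed covariates. Precision may be lost even when the arms are balanced.

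The loss cannot be sized from the documents. For an assumed partial correlation of 0 to 0.4, adding pre-operative Hb to day-1 Hb lowers residual variance by 0 to 16%. These figures assume linear relations and similar slopes across arms. They are measured against a day-1-adjusted model. Moving from the change score to day-1 adjustment brings a further gain of (σX − ρσY)², also unknown here. The stated sample size reproduces and need not change.

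**What to change.** In section 9.1, before unblinding:

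1. Define baseline Hb as the day-1 post-operative value taken before study treatment.
2. Replace the t-test with a linear model, fitted at week 3 and at week 6 in all analysed patients whatever the baseline comparison shows. Hb is the outcome; arm, day-1 Hb (continuous) and latest pre-operative Hb (continuous) are the terms.
3. Take the three pairwise contrasts, with confidence intervals, from that model.
4. Delete the imbalance-triggered switch in 9.3 and the matching sentence in 9.2. Keep the descriptive baseline comparison.

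Where the pre-operative sample was repeated after postponement, the later value is the covariate. Pre-operative Hb is absent from the patient characteristics listed in section 7.3, so check that the eCRF captures it. Missing covariate values fall under the multiple imputation that section 9.6 already provides for baseline characteristics. Whether to add the remaining minimisation factors is a separate decision.

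The cost is a short paragraph of text and about one degree of freedom per covariate. With 96 patients, three arms and two covariates, 96 − 5 = 91 residual degrees of freedom remain, against 62 for a t-test of two groups of 32, provided a common residual variance is accepted. No new visits, samples or patients are needed.
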